4. I have read and understand the information in the Investigators' Brochure (or Manufacturer's Brochure) regarding the risks and potential benefits. I agree to conduct the protocol in accordance with Good Clinical Practices (ICH-GCP), the applicable ethical principles, the Statement of Investigator (Form FDA 1572), and with local regulatory requirements. In accordance with the FDA Modernization Act, I will ensure the registration of the trial on the www.clinicaltrials.gov website.
5. I agree to maintain adequate and accurate records in accordance with CHR policies, Federal, state and local laws and regulations.

UCSF Principal Investigator

Printed Name

Signature

Date

Abstract

Title	Prospective Phase II Study of Chemoembolization with Doxorubicin-Eluting Microspheres for Liver Transplantation Candidates with Hepatocellular Carcinoma and Marginal Hepatic Reserve
Patient population	Intermediate stage, unresectable hepatocellular carcinoma (HCC) confined to the liver, without significant hepatic synthetic dysfunction
Rationale for Study	To determine whether DEB-TACE can be used safely and effectively to treat patients with liver-only HCC and baseline hepatic dysfunction, TACE is frequently offered to patients with baseline hepatic dysfunction with the purpose of diminishing hepatic tumor burden while patients await transplantation. Without this therapeutic measure, disease may progress beyond UNOS T2 criteria required for organ allocation.
Primary Objectives	
• To determine the safety of DEB-TACE in patients with HCC confined to liver who are being considered for liver transplantation• To determine the response rate to DEB-TACE by conventional and modified Response Evaluation Criteria in Solid Tumors (RECIST version 1.1, mRECIST) for treated lesions in patients with liver-only HCC who are being considered for liver transplantation
Secondary Objectives	
• To measure overall radiographic response (by RECIST v1.1 and mRECIST) 6 months after the date of the first planned DEB-TACE procedure.• To measure time to untreatable progression (TTUP). TTUP is defined as time to disease progression untreatable by liver-directed percutaneous or surgical methods.• To measure median time to progression (TTP)• To measure hepatic progression free survival (HPFS)• To measure progression free survival (PFS)• To measure overall survival (OS)• To determine the proportion of patients who remain active on the wait list for a liver transplant and eventually are transplanted.• To determine the proportion of patients who are inactivated or drop out from the wait list for any reason but transplantation.• To determine the proportions of patients who are successfully down-staged and achieve active waitlist status and eventually are transplanted.• To measure proportion with alpha-fetoprotein (AFP) response with $\geq 50\%$ decline from baseline (in patients with baseline level ≥ 20) post DEB-TACE and test for association with hepatic and overall response rate, PFS, and OS• To determine whether cardiac function changes occur as a result of DEB-TACE with doxorubicin• To obtain pharmacokinetic data for doxorubicin administered as a part of DEB-TACE procedures

Abstract

Study Design	Prospective open-label two-stage phase II clinical trial to evaluate the safety and efficacy of DEB-TACE in patients with liver-only HCC and significant hepatic dysfunction who are being considered for a liver transplant.
Number of patients	17 patients will be enrolled into the first stage of the study for safety and efficacy 34 patients will be enrolled into the second stage of the study
Duration of Therapy	Most patients will need only one DEB-TACE treatment, performed within 60 days of Screening procedures For patients that have more than one treatment, the procedure will be done about 4 weeks after the first, or previous treatment, up to 4 treatments total
Duration of Follow up	Post Treatment Evaluation will last 1 year
Duration of study	The study will reach completion 5 years from the time the study opens to accrual
Study Procedure	Doxorubicin Eluting Bead Transarterial Chemoembolization (DEB-TACE): Doxorubicin-loaded LC Beads® are administered via a co-axially placed commercially available hepatic artery catheter into hepatic arteries targeted for treatment. Procedure is performed under direct fluoroscopic visualization until stasis of arterial flow is achieved or until a total of 4 ml of microspheres have been administered, whichever occurs first.

Abstract

Safety Assessments	
• Laboratory tests (Day 1 and Day 7±3 after every DEB-TACE, then 30±7, 90±14, 180±14, 270±14, and 360±14 days after last planned DEB-TACE)• Physical exam/AE assessment (Day 1 and Day 7 after every DEB-TACE, then 30±7, 90±14, 180±14, 270±14, and 360±14 days after last planned DEB-TACE)• MELD score (30±7, 90±14, 180±14, 270±14, and 360±14 days after last planned DEB-TACE))• Imaging procedures to assess tumor burden (30±7, 90±14, 180±14, 270±14, and 360±14 days after last planned DEB-TACE)• Cardiac function monitoring by echocardiography (at baseline and approximately 30 days after last planned DEB-TACE procedure). 
Safety data will be routinely monitored and sequential safety assessments will be conducted as subjects are enrolling to the study. The study will be stopped due to safety/toxicity concern prior to interim efficacy analysis if any of the following 3 stopping rules are met:
 
1. Liver dysfunction (clinical or laboratory [total serum bilirubin], grade 4) that does not improve to baseline or </= grade 3 within 1 month following DEB-TACE in ≥ 7 patients (12% of 51 patients).
OR
2. Renal dysfunction (clinical or laboratory [serum creatinine], grade 3 or 4) that does not improve to baseline or </= grade 2 within 1 month following DEB-TACE in ≥ 2 patients (1.2% of 51 patients).
OR
3. Any grade 5 AE (death) attributed as at least possibly-related to study intervention in ≥ 3 patients (4.8% of 51 patients). 
Stopping Rules for Efficacy after 17 patients have completed last planned DEB-TACE
 
1. If four (4) or fewer responses (complete, partial, or stable disease response according to mRECIST in treated lesion(s) approximately 1 month after last planned DEB-TACE) are observed among first stage of 17 patients.

UCSF	University of California San Francisco
ULN	Upper Limit of Normal
UNOS	United Network for Organ Sharing

1.0 BACKGROUND AND RATIONALE

1.1 Background/Standard Therapies

Tumor resection or liver transplant (LT) represent the best options for cure in patients with hepatocellular carcinoma (HCC). Unfortunately, most patients are candidates for neither at the time of diagnosis (1). Depending on the extent of tumor and the overall health of the patient, those who are not able to undergo resection or transplantation may be referred for liver-directed treatments, supportive care or rarely, experimental medical protocols (2).

Liver-directed therapies have been shown to extend survival compared with supportive care (3, 4, 5), and in optimal cases may be effective in allowing “downstaging” (6, 7, 8) of the tumor to allow resection or transplantation. Moreover, liver-directed therapies have been found to diminish drop-out from the liver transplant wait list (7).

Many liver-directed therapies take advantage of the liver’s unique blood supply. Two sets of vessels bring blood to the liver: the portal vein and the hepatic artery. The portal vein brings the majority of the blood and the great majority of the nutrients to normal liver. While the hepatic artery supplies a far smaller percentage of blood to normal liver, it provides nearly all of the vascular supply to liver tumors. Hepatocellular carcinoma characteristically has a very rich arterial blood supply, providing an excellent opportunity for minimally invasive, arterially directed targeted therapies. The hepatic artery is routinely accessed using standard angiographic techniques and fluoroscopic guidance.

Liver-directed therapies may be used alone or in combination. These therapies include: percutaneous ablation (a needle-like device called an applicator is inserted into the tumor(s) under imaging guidance, energy is applied through the applicator, and tumor destruction is induced around the “needle”), arterial embolization (the blood vessels supplying the tumor are occluded with tiny particles to induce ischemia), chemoembolization (chemotherapy is delivered directly to the tumor blood vessels immediately before they are occluded), intra-arterial chemotherapy (chemotherapy is delivered directly to the liver artery supplying the tumor(s) and radioembolization (selective internal radiation therapy, SIRT) (2).

At UCSF and other transplant centers, patients with HCC confined to the liver may be offered a spot on the liver transplant list. Expected 5-year survival in patients with HCC who make it to liver transplant is 70-90%, which is better than that for surgery (50%) or liver-directed therapy alone (20-50%) (1). A chief requirement for listing is tumor burden within United Network for Organ Sharing (UNOS) T2 stage (one lesion less than 5 cm or up to 3 lesions each less than 3 cm in size). Patients with UNOS T3 stage (disease confined to the liver without evidence imaging evidence of portal or hepatic vein invasion or extracapsular extension) may also be listed if they undergo successful “down-staging” to UNOS T2 or T1 using liver-directed therapy (7, 8). Liver-directed therapy choices include transarterial chemoembolization (TACE), SIRT, radiofrequency ablation (RFA), and percutaneous ethanol injection (PEI). Typical wait for an organ in UNOS region 5, which includes California, is 1.5-2 years depending on the patient’s blood type. If untreated, HCC is likely to progress during this long waiting period beyond UNOS T2 stage. Therefore, various liver-directed treatment approaches including TACE, RFA, and PEI are

employed to maintain patients active on the transplant list.

TACE is a standard treatment option for patients with intermediate stage, unresectable hepatocellular carcinoma (HCC) without significant hepatic synthetic dysfunction (2). TACE produces an objective tumor response rate of 35%-40% and confers a significant survival advantage as compared to best supportive care (9, 3, 4). Improved quality of life and reduced pain following initiation of chemoembolization are reported among patients undergoing sequential TACE (10). Current indications for TACE include first line treatment for unresectable intermediate stage HCC, as “bridging” therapy to prevent disease progression and drop-out on the liver transplant waiting list, as a method to “down-stage” patients to qualify them for liver transplantation, or enable liver resection through the reduction of disease burden (2, 7).

TACE for HCC can be performed in a variety of ways. Conventional TACE (cTACE) is performed by dissolving one or more cytotoxic drugs including doxorubicin, cisplatin, and/or mitomycin C in iodinated contrast and adding ethiodized oil to the dissolved drugs to make a 1:1 emulsion. Following infusion of the emulsion into the hepatic artery, embolization is performed to stasis of arterial flow with a variety of permanent or dissolvable embolic agents (11).

During the past 5 years, it has been recognized that two commercially available particulate embolic agents (LC Beads[®], Biocompatibles Inc., Farnham, Surrey, UK; Hepasphere[®], Merit Medical, South Jordan, UT, USA) can be used as drug carriers by forming an ionic bond between the drug and the microsphere (12, 13). The two drugs that are currently being delivered in this fashion are doxorubicin for patients with HCC and irinotecan for patients with colorectal liver metastases. The process of performing TACE using drug-eluting beads (DEB) has become known as DEB-TACE. Pharmacokinetic studies have shown that during cTACE a substantial amount of drug is present in the systemic circulation, whereas during DEB-TACE the amount of drug in the systemic circulation is negligible (12, 13). A recently published randomized clinical trial (PRECISION V) showed that DEB-TACE using doxorubicin-eluting microspheres had similar efficacy to cTACE performed with doxorubicin and ethiodized oil emulsion (14).

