3.0 STUDY DESIGN

This is a prospective open-label two-stage phase II clinical trial to evaluate the safety and efficacy of DEB-TACE in patients with liver-only HCC and hepatic dysfunction who are being considered for a liver transplant. Seventeen patients will be enrolled during the first stage of the study for efficacy. Subsequently, 34 patients will be enrolled into the second stage of the study. Prior surgical resection or liver-directed therapy will be allowed. Patients will be followed for one year following DEB-TACE. This study will take up to five years to complete.

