8.4.1 Patients with Single DEB-TACE Procedure

The following laboratory testing will be performed 1, 7±4, 30±7, 90±14, 180±14, 270±14, and 360±14 days following DEB-TACE: CBC, coagulation panel, BUN, creatinine, and liver function tests. Serum alpha-fetoprotein testing will start approximately 30 days following last planned DEB-TACE procedure. Any abnormal lab values will be followed up as clinically indicated. Laboratory tests may be performed at UCSF or at a local lab.

Seven ±4 days following DEB-TACE patients will have clinic follow up in Interventional Radiology for toxicity monitoring including reviewing the laboratory results above. Any expected or unexpected AEs will be discussed with the study PI or a designated co-investigator. Further testing and/or treatment will be coordinated by the study PI or a designated co-investigator if clinically appropriate (see section 7).

Cardiac function assessment monitoring using echocardiogram will be obtained approximately 30 days following the DEB-TACE procedure.

Patients will be seen in clinic approximately one month after the DEB-TACE procedure. During this visit, interim medical history will be obtained, and a physical examination will be performed. This will include (but will not be limited to) cardiopulmonary evaluation and an abdominal exam. Subsequently, patients will be followed in clinic at approximately 3 month intervals until 360 days following DEB-TACE.

Approximately one month after DEB-TACE procedure, patients will undergo repeat cross-sectional imaging with multi-phase contrast-enhanced CT or MRI of the abdomen. Subsequent imaging will be performed at approximately 3 month-intervals until 360 days following DEB-TACE. Standard clinical practices will be adhered to during the follow-up period.

Response to treatment will be assessed according to the RECIST version 1.1 and mRECIST criteria (see section 9.2).

Patients will be removed from study and follow-up assessments will stop prior to 360 days following DEB-TACE if a patient:

- a) requires > 4 DEB-TACE procedures
- b) requires another anti-cancer treatment modality such as ablation, surgery, or conventional TACE
- c) receives a liver transplant
- d) develops untreatable intrahepatic or extrahepatic disease progression
- e) experiences unacceptable toxicity (see section 10.0). All serious adverse events will be followed until the SAE has been resolved.

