10.3 CRITERIA FOR PATIENT REMOVAL FROM STUDY

Patients will be removed from study for any of the following events:

- Unacceptable toxicity (listed above in section 10.1),
- Other toxicity which investigator deems to place the patient at significant risk for toxicity
- Withdrawal of consent
- Noncompliance or inability to meet requirements of protocol
- Requirement for >4 DEB-TACE procedures
- Requirement for another anti-cancer treatment modality such as ablation, surgery, conventional TACE
- Receives a liver transplant
- Develops untreatable intrahepatic tumor progression
- Develops extrahepatic tumor progression

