4. Hepatic progression-free survival (HPFS). Hepatic progression-free survival rate will be defined as the number of patients who neither progressed in the treated regions of the liver (using RECIST 1.1 and mRECIST) nor died before 1, 3, 6, 9, and 12 months after date of last DEB-TACE over the number of patients who entered the trial at these same timepoints. Estimates of the HPFS curves from the Kaplan-Meier method will be presented. Median progression event time and a 2-sided 95% confidence interval for the median will be provided using a normal approximation. For each stratum, the median, 25th and 75th percentile for HPFS will be provided.
5. Progression-free survival (PFS). Progression-free survival rate will be defined as the number of patients who neither progressed (using RECIST 1.1 and mRECIST) nor died before 1, 3, 6, 9, and 12 months after date of last DEB-TACE over the number of patients who entered the trial at these same timepoints. Estimates of the PFS curves from the Kaplan-Meier method will be presented. Median progression event time and a 2-sided 95% confidence interval for the median will be provided using a normal approximation. For each stratum, the median, 25th and 75th percentile for PFS will be provided.
6. Overall Survival (OS) is a secondary efficacy endpoint and will be analyzed 12 months after the last patient is enrolled. OS will be calculated from date of first DEB-TACE until date of death, using chart review and/or follow up phone calls to determine date of death in patients after removal from study. The survival of patients who are permanently lost to follow-up or still alive after 360 days of follow up post study discontinuation will be censored on the date the patient is last-contacted or last known to be alive. Estimates of the OS curves from the Kaplan-Meier method will be presented.
7. Proportion of patients who remain active on the waitlist and are eventually transplanted is a secondary clinical endpoint. This data will be presented using Kaplan-Meier method
8. Proportion of patients who are inactivated or drop out from the wait list for any reason but transplantation will be determined. Reasons for inactivation and/or removal from waitlist will be tabulated.
9. Proportions of patients who are successfully down-staged and achieve active waitlist status and eventually are transplanted will be determined.

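### Wait-list endpoints 7 to 9 have no horizon, and planned follow-up stops short of the protocol's own typical wait, so many and possibly most transplants could be missed

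*Combined protocol and SAP*

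**What the plan says.** **The wait.** Section 1.1: "Typical wait for an organ in UNOS region 5, which includes California, is 1.5-2 years". The same paragraph says that tumours left untreated are likely to grow beyond stage T2 over that period. It names TACE, RFA and PEI as the means of keeping patients active on the list.

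**The endpoints.** Section 12.3, endpoint 7: "Proportion of patients who remain active on the waitlist and are eventually transplanted is a secondary clinical endpoint", to be shown by Kaplan-Meier. Endpoint 8 is the proportion inactivated or dropped from the list for reasons other than transplant. Endpoint 9 is the proportion down-staged, made active on the list and eventually transplanted. None of the three has a time origin, a horizon or a data cut-off.

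**The follow-up.** Abstract: "Post Treatment Evaluation will last 1 year". Section 3.0: "Patients will be followed for one year following DEB-TACE". The Abstract and section 8.4.2 count the visits from the last planned procedure, out to day 360.

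**The early stop.** Section 8.4.1: "Patients will be removed from study and follow-up assessments will stop prior to 360 days following DEB-TACE if a patient" meets one of several conditions, including "requires another anti-cancer treatment modality such as ablation, surgery, or conventional TACE". Section 8.4.2 has the same list, and section 10.3 repeats the rule: "Requirement for another anti-cancer treatment modality such as ablation, surgery, conventional TACE". More than four DEB-TACE procedures, untreatable progression, unacceptable toxicity and transplant also end follow-up.

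**After removal.** Under overall survival, section 12.3 plans "using chart review and/or follow up phone calls to determine date of death in patients after removal from study". Sections 8.4.1 and 8.4.2 also provide for review of the explant pathology report in transplanted patients. No section describes collecting listing, inactivation or delisting after removal.

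**The concern.** An endpoint about who is eventually transplanted needs observation that reaches the time when transplants usually happen. Here the scheduled observation stops before the lower end of the wait that the protocol itself quotes.

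The early stop adds a second problem. Ablation and conventional TACE are ordinary bridging care in section 1.1, yet needing either one ends follow-up. Such a patient may still be listed and may later be transplanted or delisted. Treating that patient as censored in the Kaplan-Meier analysis of endpoint 7 assumes the same prospects as patients who stay on study. That is doubtful, because the reason for removal is the state of the tumour. Untreatable progression also ends follow-up and plausibly precedes delisting, so endpoint 8 can lose events too.

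At stake are three stated secondary objectives. They bear directly on the rationale in section 1.6, which is to limit tumour burden while patients wait for an organ.

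**Working it through.** **Inputs from the documents**
- Typical wait *w* = 18 to 24 months (1.1). It is not said to be a mean or a median, and its starting point is not given.
- Follow-up *t* = 12 months after the last planned DEB-TACE (Abstract, 8.4.2).
- Longest time from the first DEB-TACE: section 8.4.2 requires the first follow-up imaging within 6 months of the first procedure, about 1 month after the last one. The last procedure therefore falls at about month 5, and 5 + 12 = 17 months, which is below 18.
- Patients may be listed or only screened at entry (4.2). Elapsed wait and expected drop-out are not given.

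The plan has no figure of its own for these endpoints. Its two-stage design reproduces: stage 1 stopping 75.8% and 12.6% (stated 76% and 13%), exact type I error 4.87%, power 85.4%. Nothing below changes it.

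**Share of transplants later than 12 months**

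| Assumption | Formula | *w* = 18 | *w* = 24 |
|---|---|---|---|
| Constant rate, *w* a median, no drop-out | 2^(-12/*w*) | 63% | 71% |
| Constant rate, *w* a mean, no drop-out | exp(-12/*w*) | 51% | 61% |
| *w* a median, assumed 25% drop-out by 12 months | 2^(-12/*w*) × 0.75 | 0.630 × 0.75 = 47% | 0.707 × 0.75 = 53% |
| Fixed wait, elapsed part uniform on 0 to *w* | 1 - 12/*w* | 33% | 50% |
| Fixed wait starting at DEB-TACE | none occur by 12 months | 100% | 100% |

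In the third row drop-out is a competing constant hazard. The share of eventual transplants still to come at 12 months is then the probability of being event-free, which is the product shown.

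With *t* = 17 months, the longest course, the first row becomes 52% to 61% and the second 39% to 49%.

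**Transplants seen on study if removal competes.** The documents give no removal rate, so assume that 10% to 50% are removed for other therapy within 12 months. With λ = ln 2/*w* for transplant and ρ = -ln(1 - removal)/12, the share seen is λ/(λ + ρ) × [1 - exp(-12(λ + ρ))].
- *w* = 18, 10% removed: 35%, about 18 of 51.
- *w* = 24, 50% removed: 22%, about 11 of 51.

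**Kaplan-Meier with drop-out censored.** Keep the assumed 25% drop-out, so δ = -ln(0.75)/12 = 0.0240 per month. Kaplan-Meier for transplant estimates 1 - 2^(-12/*w*), which is 37.0% (*w* = 18) or 29.3% (*w* = 24). The proportion actually transplanted by 12 months is λ/(λ + δ) × [1 - exp(-12(λ + δ))]:
- *w* = 18: 0.0385/0.0625 × 0.528 = 32.5%.
- *w* = 24: 0.0289/0.0529 × 0.470 = 25.7%.

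So even without informative removal, Kaplan-Meier overstates the proportion transplanted when drop-out is treated as censoring.

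**The case against.** The strongest reply is that the wait is a regional background figure that varies with blood type, not a planning input for this population. Patients already listed at entry have used up part of it. Drop-out also competes with transplant and lowers the share of transplants that come late. This stands, and it is why the size is given as a range. It does not remove the problem, because the most favourable row still leaves a third of transplants after 12 months. Nor can that row apply to everyone: some patients are only screened at entry, and under section 1.1 T3 patients are listed only after successful down-staging. For those in endpoint 9 the listing clock generally starts after treatment.

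Second, the documents do not fix a 360-day window for endpoints 7 to 9. The one-year limit is written into TTUP and TTP, and what stops at removal is the follow-up assessments. That is also correct, but silence does not provide data: no other collection of list status is described.

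Third, transplant is itself a removal event, so transplants on study are recorded, and explant reports are reviewed. A reader might infer that overall survival alone draws on records after removal; the explant review shows otherwise. However, it has no stated window and says nothing about inactivation, delisting or patients still waiting.

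Fourth, these are descriptive secondary endpoints with no role in the sample size or the stopping rules. That is so, and it limits the weight of the point.

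**Conclusion.** The point holds as a gap between the wait-list endpoints and the data the plan says it will collect. As written, many and possibly most transplants, and some delistings, would go unrecorded, and censoring at removal for other therapy would be informative.

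The share of transplants after 12 months runs from 33% to 71% across the four main readings, and is 100% if a fixed wait starts at DEB-TACE. Which reading applies depends on elapsed wait and drop-out, and the documents give neither.

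Two stronger readings are tempting and not supported. A reader might infer that most transplants will certainly be missed. The 63%-71% figure needs a median wait starting at DEB-TACE and no drop-out. A reader might also infer that the trial cannot answer its wait-list questions at all. Drop-outs and transplants during follow-up can be seen, and the waiting-time arithmetic does not bear directly on endpoint 8. The direction of bias from removal for other therapy is not established either, since no removal rate is given. The primary endpoint and N = 51 are unaffected.

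**What to change.** In sections 8.4 and 12.3:

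1. Extend the chart review already planned for overall survival to record dates of listing, inactivation, delisting and transplant for every treated patient, including those removed from study, up to one common data cut-off at study closure.
2. Measure time from the first DEB-TACE. For endpoint 9, also report from listing.
3. Do not censor at removal for other therapy. Censor administratively at the cut-off.
4. Replace Kaplan-Meier for endpoint 7 with cumulative incidence of transplant, and of drop-out or death, as competing events. Report at fixed times, for example 12 and 24 months, and state endpoints 8 and 9 at the same times.

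The cost is a few more items in an existing chart review at a single transplant centre, with no added visits or scans. Late enrollees will have shorter follow-up at a common cut-off. Administrative censoring handles this, but the 24-month estimates will rest on fewer patients.
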